4. Recently started purulent sputum, or changes in the characteristics of the sputum, or an increase of respiratory secretions, or an increase in endotracheal aspiration needs.

5. The starting or worsening of coughing, or of respiratory difficulties.

6. Rales.

7. Worsening of the blood gases exchange: Oxygenation index >3 or a drop of it in relation to previous measurements and/or a Kirby index <300 or a drop of it in relation to previous measurements. Both determinations indicate a worsening of respiratory functions.

- 2. Patients aged 0 to 8 years old.
- 3. A minimum HS of 72 hours.
- 4. Having informed consent.
- 5. Not having had previous RPP treatment.

Deferral criteria:

1. Presenting a fever state for more than three days. Performing physiotherapy increases the body's peripheral temperature.

- 2. Presenting an oxygen saturation below 80%.
- 3. Requiring mechanical ventilation.
- 4. Hemodynamic instability.
- 5. Presenting systemic inflammatory response syndrome.
- 6. Inotropic support.
- 7. Anatomical variants in the thorax.
- 8. Unstable thorax.
- 9. Esophageal atresia.
- 10. Pleural effusion, pneumothorax.
- 11. Alterations that compromise respiratory centers and/or the phrenic nerve.
- 12. Neuromuscular diseases that compromise respiratory mechanics.

Elimination criteria:

The existence of one or more of the following:

- 1. Refusal to colaboration by the responsible person or patient.
- 2. Barotrauma.
- 3. Ascites (grave).
- 4. Focal lung pneumatosis
- 5. Pulmonary embolism (contraindication of the thoracic physiotherapy maneuvers).
- 6. Tumors in the upper respiratory system, intra or extrathoracic.
- 7. Glossitis.
- 8. Immediate or mediate postoperative state of head, abdomen or thorax.
- 9. Use of mechanical ventilation.
- 10. Paient with cystic fibrosis

Inervention group

The intervention group (IG) will be subject to RPP. Techniques of slow expiration will be used (PSE and TP) and slow inspiration (CEFE) for the sweeping of secretions, during its expulsion forced expiratory techniques will be used (tracheal reflex).

10 sessions will be performed, one a day from Monday to Friday, with a duration of 10 to 15

minutes.

Intervention maneuvers

RPP consists of two steps, 1.the sweeping or detachment of secretions and 2.the expulsion of the secretions.

a. Prolonged slow expiration (PSE)

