- 2. Days of hospital stay from the beginning of the pneumonia.

Confounding variables

- 1. Baseline disease.
- 2. Age.
- 3. Nutritional state.

Descriptive variables

- 1. Sex.
- 2. Reasons for check-in.
- 3. Heart rate.
- 4. Oxygen saturation (SaO2).
- 5. Lung occupancy.
- 6. Wang score.

Variables	Туре	Instrument	Range
Clinical severity.*	Ordinal.	Wang score.	0-12 pts.
Heart rate.*	Discrete quantitative.	Pulse oximeter. ChoiceMMed MD300C5.	30bpm to 325bpm.
SaO ₂ .*	Discrete quantitative.	Pulse oximeter . ChoiceMMed MD300C5.	0% to 100%.
Lung occupancy.**	Nominal.	Simple X-ray of the thorax.	Identification of the percentage occupied by secretions and infiltrates, detect complications (atelectasis, effusion ,etc).
Days of hospital stay from the beginning of the pneumonia.**	Discrete quantitative.	Clinical file.	0-180 days.
Age.***	Discrete quantitative.	Clinical file.	1 to 6 years 364 days old.
Sex.***	Nominal	Clinical file.	Masculine/femenine.
Baseline disease.	Nominal.	Clinical file.	Yes/No Specify.
Reason for check-in.***	Nominal	Clinical file.	Specify.
Complications of pneumonia from the momento of inclusion.***	Nominal.	Clinical file.	None/ Effusion/ Necrosis or pulmonary abscess/ Other (specify)

*Measurements must be performed before intervention, immediately after, and 15, 30 and 150 minutes after. **Measurements will be performed before

initiating treatment sessions and after they conclude. *** Measurements will be developed previously to the randomized group assignation.

GENERAL DESCRIPTION OF THE STUDY

Assessment prior to the study

- 1. All patients diagnosed with pneumonia who comply with the selection criteria will be invited to participate in the study, in case of accepting, those older than 8 years old will verbally agree and will be given forms of informed consent to sign.
- 2. Data obtained will be documented in a previously established data collection format (Anex 2).
- 3. If there is no contraindication for the procedure, then the maneuver will be assigned.

Initiation and evaluation of the assigned maneuver

- 1. The researcher will perform the maneuver according to group assignation.
- 2. Subsequently a collaborator, previously blinded to the maneuver and standardized for the Wang score (a modification of the Silverman score), will evaluate the Wang score 15, 30 and 150 minutes after its application.

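### The variable for complications arising from inclusion onward is marked as measured before random assignment; secondarily, the timing of the elimination list and the analysis population are not stated

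*Combined protocol and SAP*

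**What the plan says.** **Complications.** The table under Research variables includes "Complications of pneumonia from the momento of inclusion", taken from the clinical file, with the options "None/ Effusion/ Necrosis or pulmonary abscess/ Other (specify"). It carries three asterisks, which the footnote explains as "Measurements will be developed previously to the randomized group assignation". One asterisk means readings around each session. Two mean before the sessions begin and after they conclude.

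**Lung occupancy.** This separate row has two asterisks, and its range column mentions detecting complications such as atelectasis and effusion. The list of complementary measurements under Variables and measuring instruments ties the same variable to the x-ray taken at diagnosis.

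**Eligibility lists.** Under Selection criteria, the deferral list includes "3. Requiring mechanical ventilation" and "10. Pleural effusion, pneumothorax". The elimination list includes "1. Refusal to colaboration by the responsible person or patient", barotrauma, "5. Pulmonary embolism (contraindication of the thoracic physiotherapy maneuvers") and "9. Use of mechanical ventilation". Its lead-in says only that one or more of the items exists. It gives no time point and no consequence.

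**Analysis and follow-up.** The Data analysis plan specifies a Mann-Whitney U test and names no analysis population. A collaborator registers hospital stay, and the study ends when the child leaves hospital.

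**The concern.** The name of the complications variable and its timing mark cannot both be followed. If the data form follows the mark, the one variable named for complications after entry becomes a baseline description. A difference between arms after assignment, whether benefit or harm, would not appear in it. This matters in a trial of manual chest techniques in sick children, where such a comparison would be expected in the report.

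The elimination list raises a second, less certain matter. The Problem statement names mechanical ventilation as a possible consequence of uncontrolled secretions, which the intervention is meant to control. If ventilated children were taken out of the analysis after assignment, the comparison would be conditioned on an event related to the treatment's target. The distortion could go either way. More removals under physiotherapy would look like benefit, and fewer would hide a real one.

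**Working it through.** **1. Complications: name against mark.** The other rows with three asterisks are age, sex and reason for check-in. All three are fixed at entry and fit a measurement made before assignment. The complications row does not, because its period opens at inclusion and a pre-assignment reading captures little or none of it. No existing mark fits either: one asterisk is tied to single sessions, two to the start and end of the session course, three to before assignment. None means from assignment to discharge.

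**2. Does lung occupancy fill the gap?** Only in part. Its two asterisks would allow a reading after the sessions, and effusion or atelectasis could then be seen. But it covers radiographic findings only, and the complementary-measurements list ties it to the diagnostic film. It has its own conflict and does not resolve this one.

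**3. Elimination: the two readings.**
- *Before entry only.* The list stands under Selection criteria. The assessment steps screen children and check for contraindications before the maneuver is assigned. Pulmonary embolism is labelled a contraindication. Cystic fibrosis, tumours and postoperative state are screening items. Ventilation can count as a diagnostic finding for inclusion, which gives a reason to screen for it.
- *Also after assignment.* Ventilation is already a deferral item and consent is already an inclusion item, so listing ventilation and refusal again adds little if both lists apply only at entry. Refusal, barotrauma and ventilation can each arise later.

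The text does not choose between them.

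**4. The plan's own figure.** With a difference of 1.5, SD 2.6, one-sided alpha 0.05 and power 80%:

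n = 2 × 2.6² × (1.645 + 0.842)² / 1.5² = 37.15, so 38 per group.

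Dividing 37.15 by 0.955, the Mann-Whitney efficiency for normal data, gives 38.9, so 39. The stated 40 is reproduced. This uses the squared sum of z values; the printed formula omits the square, which is a separate matter. Power at 40 per group is 82.5%.

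**5. Scale, on assumptions only.** The documents give no removal rate and no deletion rule.
- *Equal removal, unrelated to outcome.* At 5%, 10%, 15% or 20%, there remain 38, 36, 34 or 32 per group, with power 80.8%, 78.9%, 76.8% or 74.6%. There is no bias.
- *Unequal removal.* If removed children score k points worse than those retained, the group difference shifts by (p₁ − p₂) × k. With a rate gap of 5 to 10 percentage points and k of 2.6 to 5.2, that is 0.05 × 2.6 = 0.13 to 0.10 × 5.2 = 0.52 points, against a planned 1.5.
- *Type I error.* The simulation assumed 40 per arm, a Wang mean of 6 and SD 2.6 rounded and limited to 0–12, one score per child, and whole children deleted at 10% under physiotherapy against 5% under control. With no true effect, a correlation of 0.3 to 0.5 between removal and score gave an apparent benefit of 0.06 to 0.11 points and a one-sided error of 6.4% to 7.4%. At correlation 0 it was 5.0%. At correlation 1, where the score alone decides removal, it was 10.2%.

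**The case against.** The strongest reply on complications is that this is one misplaced mark in a loosely drafted, translated table. The baseline-disease row has no mark at all. The lung-occupancy row already offers a route to later complications, and the data form (Anex 2) is not available to check. Much of this stands. A reader might infer that complications after assignment cannot be recorded anywhere, and the documents do not support that, because of the lung-occupancy row. A reader might also take the effusion option as proof that the mark is wrong, since effusion is a deferral item. That goes too far: deferral is not defined as permanent exclusion, so an earlier effusion could be noted at entry. What does not fall is the conflict itself, because a stated timing rule contradicts the variable it governs.

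On elimination, the reply is that most items read as screening conditions and that a condition listed twice is weak evidence of removal after randomisation. That is fair. Hospital stay is followed to discharge with no stated exception for eliminated children. The model behind the figures also uses the score level, whereas the trial is sized on a decrease in score, and need for ventilation may follow the level more closely than a 30-minute change.

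**Conclusion.** The complications conflict holds on the text alone and needs no assumption. As marked, this variable would not capture or compare by arm any complication arising after assignment. It should be corrected, and doing so is cheap.

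The elimination list is a real ambiguity and a lesser point. A reader might infer that the protocol deletes ventilated or refusing children from the analysis and so inflates type I error or shortens the recorded stay. The documents do not support that: no passage states a deletion rule, and a pre-entry reading is plausible. Every bias figure above rests on assumed rates, imbalance and correlation. They show only that the effect on the Wang comparison would be small beside 1.5 points at moderate correlation, and nil if removal is confined to screening, equal by arm in rate and kind, or unrelated to outcome. The missing analysis population and the missing rule for in-hospital death in the day count are gaps under either reading.

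**What to change.** 1. Change the timing mark on the complications row, with a new footnote definition, so that complications are taken from the clinical file from assignment to discharge and reported by arm.
2. Reconcile the deferral and elimination lists by stating, item by item, whether each applies before assignment, after it, or both. What happens clinically after such an event, including whether sessions continue, is for the protocol to state.
3. State that all randomised children are analysed in their assigned group, using the Wang scores already taken and hospital stay from the clinical file, subject to consent where a family refuses.
4. State that an in-hospital death is not counted as a short stay.
5. Report withdrawals after assignment by arm, with reasons.

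The cost is protocol wording and one added definition. Complications and stay already come from the clinical file, and follow-up already runs to discharge. The one real addition is a rule for missing later Wang scores, which has to be written before the data are seen.

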The OBJECTIVE of this research protocol is to evaluate the effectiveness of RPP compared to postural drainage plus compression to the muscle belly of the upper limbs, as an adjuvant treatment for children with pneumonia. It is expected that the clinical severity decreases by 1.5 in the Wang score (a modification of the Silverman score), with a standard deviation of 2.6 points and a decrease of two days in the hospital stay with a α 0.05 in a one-tail test, a P of 80% and a 95.5% confidence interval.

METHODOLOGY, the protocol design corresponds to a single-blind trial. The population will consist of children aged from 0 to 8 years old diagnosed with pneumonia with a development time less than 7 days. The participants who comply with the selection criteria will be grouped in blocks of two using a randomization software (www.radomization.com).

The sample calculation corresponds to 40 participants per group. The intervention group will be exposed to techniques such as prolonged slow expiration, controlled expiratory flow exercises, tracheal pumping and tracheal reflex. The control group will be subject to postural drainage plus compressions to the muscle belly of the upper limbs. Both groups will go through 10 sessions: One daily session from Monday to Friday with a duration of 10 to 15 minutes each.

The Wang score (a modification of the Silverman score) will be used to measure the clinical severity and a pulse oximeter ChoiceMMed MD300C5 for SpO_2 and heart rate readings, the medical records will be consulted during the hospital stay.

DATA ANALYSIS PLAN, to prove whether there are or not statistical differences in and between both groups a Mann-Whitney U test will be used. The weightings from the Wang score (a modification of the Silverman score) will be considered before and immediately after the intervention maneuvers, and after 15, 30 and 120 minutes after said maneuvers have been performed.

BACKGROUND

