RPP stimulates the control of secretion accumulation modifying pleural and intraalveolar pressure and pulmonary volumes through passive, active-assisted or active contractions of the inspiratory and expiratory muscles, altering the line of air flow at will. RPP consists of two stages:

1. Secretion sweeping: Secretions generate resistance to the line of air flow, turning laminar flow into turbulent flow. The handling at will of inspiration and expiration time increases the intensity of the turbulence and cilia movement, causing the secretions to detach due to the transmission of energy described by Newton's third law in the zones where secretions and line of air flow make contact.

prolonged slow expiration, FET and controlled expiratory flow exercises will be used.

2. Secretion expulsion: The expelling of secretions through the airways is wanted by stimulating deglutition and active or assisted coughing. Tracheal pumping will be used.

The control of secretion accumulation in the broncho-pulmonary airway network tends to decrease air flow resistance and respiratory frequency (RF), and to regain alveolar space, normalizing inspiration time, bronchial permeability and pulmonary mechanics.

The effectiveness of said techniques has not been proved, since present evidence combines them with techniques designed for adult patients.

Research questions:

1. What is the effectiveness of RPP in comparison to postural drainage (PD) plus muscle belly compressions to the upper limbs for the reduction of clinical severity (in Wang score (a modification of the Silverman score)) for a child with pneumonia, 15, 30 and 150 minutes after it is performed?

2. What is the effectiveness of RPP compared to PD plus muscle belly compressions to the upper limbs for the decrease in days of hospital stay for children with pneumonia?

JUSTIFICATION

25% of nosocomial infections in our country are in-hospital pneumonia.

In-hospital pneumonia increases hospital stay by 5 days on average and increases hospitalization costs.

If respiratory pediatric physiotherapy is proven to be useful, days in hospital stay and hospitalization costs may decrease.

Not performing this research protocol will promote the empirical prescription of said techniques by the public health system.

OBJECTIVES

General objective

To evaluate the effectiveness of RPP compared to PD plus muscle belly compressions to the upper limbs for the treatment of a child with pneumonia.

Specific objectives

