To evaluate the prolonged effects (15, 30 and 150 minutes after intervention) of RPP on clinical severity (Wang score (a modification of the Silverman score)) in comparison to PD plus muscle belly compressions to the upper limbs for the treatment of a child with in-hospital pneumonia.

To evaluate the effect of RPP compared to PD plus muscle belly compressions to the upper limbs on the number of days of HS of children with pneumonia.

HYPOTHESIS

1. Children with pneumonia who receive RPP Will have a decrease of 1.5 points, with a standard deviation of 2.6 In the Wang score (a modification of the Silverman score), 30 minutes after it being performed.

2. Children with pneumonia will have a decrease in HS of two days, compared to those treated with PD plus muscle belly compressions to the upper limbs.

METHODOLOGY AND RESEARCH DESIGN

DESIGN

Single-blind randomized clinical trial

Population

1. Study universe: Hospitalized children with pneumonia at the infectiology service.

2. Study population: Children from 0 to 8 years old with a diagnostic of pneumonia (under WHO's criteria) with a development time less than 7 days.

3. Sample: With the support of the epidemiology department, a daily list of all new cases of pneumonia will be provided. Patients then will be included once the diagnostic established by the pneumonia infectiology service is obtained.

Sample size calculation

The calculation for a sample size for an error of α 0.05 in a one-tail test and a power of 80% is based on the values described by Postiaux^{*37} in the difference between the groups 30 minutes after the intervention, during 10 sessions. The difference in the Wang score (a modification of the Silverman score) measurements between the two groups was of 1.5 points with a standard deviation of 2.6 points.

 $\label{eq:states} \begin{array}{l} \Delta \texttt{= 1.5} \\ \texttt{S= 2.6} \\ \texttt{n = 2S}^2(\texttt{Z}_{\alpha/2} + \texttt{Z}_\beta)/\Delta^2 \end{array}$

The participants' sample size will be of 40 per group, to obtain statistical differences in the decrease of the Wang score (a modification of the Silverman score) entre between both groups with a α 0.05 in a one-tail test and a power of 80%, considering a decrease of 36% and a standard deviation of 13%.

Randomization

- 1. A sequence of aleatory numbers in blocks of 2 will be generated in each of the study groups using the software randomization.com, done by a person foreign to the research.

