Also accepted as the term expiratory flow acceleration (EFA). It is obtained by the energetic contraction of the expiratory muscles (mainly the abdominal ones). During the maneuver, the intrathoracic pressure of the oral discharge increases simultaneously, which produces a lower mouth discharge that that of coughing, that allows the tearing off of the secretions from the bronchial wall due to the apparition mechanism of the SPP (same pressure point). This situation responds to the function of viscosity, elasticity, mucus thickness, the level of adhesion to the bronchial wall and the flexibility of the bronchial wall.^{*36}

Control Group

The control group (CG) will be subject to PD plus muscle belly compressions of the upper limbs for 10 sessions, one session a day from Monday to Friday, with a duration de 10 to 15 minutes per patient. Both groups will receive the usual treatment for pneumonia prescribed by their treating doctor.

Variables and measuring instruments.

Measurements will be performed before, and 15, 30 and 150 minutes after the maneuvers. Clinical severity will be measured using the Wang score (a modification of the Silverman score) *(Table 3)*, which consists of 4 items:

- 1. Respiratory rate.
- 2. Wheezing.
- 3. Retraction.
- 4. General condition.

Every item has an ordinal measurement level of 0 to 3 points (possible values: 0,1,2,3), excluding general condition (with a value of 0 or 3 only).

With a maximum summation of 12 points and a minimum of 0 points. The higher the score, the higher the clinical severity.

Complementary measurements:

- 1. Heart rate.
- 2. SaO₂.
- 3. Lung occupancy in the x-ray that was taken when the diagnosis was made.

The results from the pediatric Wang score (a modification of the Silverman score) will be compared in and between the groups at the following moments: 1.Before intervention (baseline state), 2.immediately after intervention, 3.15 minutes after intervention and 4.30 minutes after that.

The following tool (anex 2) has been designed to measure the variables. The

resources needed for research development are:

- 1. Medical history.
- 2. Vital signs monitors.
- 3. Stethoscope.
- 4. Pulse oximeter.
- 5. Disposable latex gloves.
- 6. Mechanical aspiration

RESEARCH VARIABLES

Independent variables

- 1. Pediatric respiratory physiotherapy.
- 2. Postural drainage plus muscle belly compressions to the upper limbs.

Dependent variables

- 1. Clinical severity.

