- 3. Another collaborator will do a follow-up on the patients in order to register their hospital stay time posterior to the diagnosis of pneumonia.
- 4. The assigned maneuver will be performed once a day on the patient.

End of study

The study will end once the patient checks out of the hospital.

Quality control

The assessment of the efficiency will be performed by 2 collaborators blinded to the maneuver. One collaborator will assess the Wang score (a modification of the Silverman score), heart rate and SaO_2 and the other collaborator will register the days of HS.

DATA ANALYSIS PLAN

Descriptive statistic: There will be an assessment of the central tendency values, relative dispersion and disposition to evaluate the descriptive variables at the start and at the end of the studyin both groups, as well as the dependent variables after the intervention.

Inferential statistic:

- 1. The comparison in score of the descriptive variables in and between the groups will be performed using a Mann-Whitney U test.
- 2. A 95% confidence Interval is estimated.

The Wang score rates will be assessed in the measurements made before and immediately after the intervention, and 13, 30 and 150 minutes after.

To describe the measurement differences and to reject or not the hypothesis, a Mann-Whitney U test will be used.

LIMITATIONS OF THE STUDY

Due to the maneuver condition, the subject cannot be blinded, and only the researchers will be single-blinded, which confers a type of bias to the study.

TIMELINE

The timeline of activities is presented as a FORMAT ATTACHED to this document.

ETHICAL CONSIDERATIONS

The 2016 guide for the evaluation of ethical considerations of our institution is presented as a FORMAT ATTACHED to this document.

Beneficence/Nonmaleficence

This is a MAXIMUM TO MINIMAL RISK study for participants, and it could cause reflux, vomit or irritability of the patient's emotional state (with all that implies). Potential benefit to the patient by improving their clinical severity and reducing the days of hospital stay. Potential Benefit to society by reducing the days of hospital stay, which in turn will reduce the cost of treatment for children with pneumonia.

Autonomy and respect

It will be clearly expressed to the patient or person responsible for them, every procedure they will become subject to, until their understanding is secured.

A Form of Informed Consent will be required (Anex 3).

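### Within-group before/after Wang scores are assigned Mann-Whitney U, an independent-samples test, although the same children are measured each time; a paired test is needed

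*Combined protocol and SAP*

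**What the plan says.** The Data Analysis Plan (Inferential statistic) reads: "The comparison in score of the descriptive variables in and between the groups will be performed using a Mann-Whitney U test". The Summary gives the same rule: "to prove whether there are or not statistical differences in and between both groups a Mann-Whitney U test will be used". Mann-Whitney U is also the only test named for deciding on the hypothesis. No paired or repeated-measures method appears in the document.

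Three places show what the within-group comparison is:

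- Research Variables lists the Wang score as the sixth descriptive variable, so the sentence in the analysis plan covers it.
- Variables and Measuring Instruments says the Wang results "will be compared in and between the groups at the following moments: 1.Before intervention (baseline state), 2.immediately after intervention", and then goes on to later times. The Summary agrees: "The weightings from the Wang score (a modification of the Silverman score) will be considered before and immediately after the intervention maneuvers", followed by later times.
- The footnote to the variables table, which applies to clinical severity, heart rate and SaO2, says: "Measurements must be performed before intervention, immediately after, and 15, 30 and 150 minutes after".

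The main question is between groups. Research question 1 asks "What is the effectiveness of RPP in comparison to postural drainage (PD) plus muscle belly compressions to the upper limbs", and the sample size of 40 per group is meant "to obtain statistical differences in the decrease of the Wang score" between the two groups.

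**The concern.** Mann-Whitney U assumes two independent samples. Scores of one child before and after a maneuver are not independent. The test ignores the pairing, so it uses the wrong variance for the difference and its p-values are wrong.

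If a child's scores are positively correlated, as expected over minutes to a few hours, the p-values are too large. A real fall within a group can then be missed. This has some weight because hypothesis 1 describes a 1.5-point fall in children given RPP without naming a comparator, so a reader may take the within-group result as evidence on it. An analyst who noticed the problem later and switched to a paired test would be departing from the plan.

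**Working it through.** **Inputs from the documents.** 40 per group; alpha 0.05, one-sided; power 80%; difference 1.5 points; SD 2.6 (Sample Size Calculation); score range 0-12 (Variables and Measuring Instruments).

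**Assumptions.** Before/after correlation ρ of 0.3, 0.5 or 0.7; mean score before the maneuver of 6 or 4; an illustrative 1-point fall. The protocol gives 1.5 and 2.6 for a between-group difference, so using them for a within-group fall is also an assumption. So is applying the one-sided level to the within-group tests.

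**1. The plan's own figure.** The standard one-sided formula gives n = 2 × [2.6 × (1.645 + 0.842)/1.5]² = 37.2, so 38 per group. Dividing by the Mann-Whitney relative efficiency 3/π gives 38.9, so 39. The stated 40 is reproduced within two patients. It rests on an independent comparison and does not depend on the pairing.

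**2. Type I error, approximate.** With n pairs and score SD s, the mean difference has variance 2s²(1−ρ)/n, but an unpaired test assumes 2s²/n. Under no change the standardised statistic therefore has SD √(1−ρ), and the true one-sided error is 1 − Φ(1.645/√(1−ρ)):

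- ρ = 0.3: 1 − Φ(1.966) = 2.5%
- ρ = 0.5: 1 − Φ(2.326) = 1.0%
- ρ = 0.7: 1 − Φ(3.003) = 0.1%

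**3. Type I error, simulated.** 10,000 replicates of 40 pairs; correlated normal values rounded and clipped to 0-12; signed-rank with zeros dropped and tie correction. Ranges cover both assumed means and both readings of 2.6: as the SD of the score, or as the SD of change. Under the second reading the score SD is 2.6/√(2(1−ρ)) = 2.20, 2.60 or 3.36.

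- Mann-Whitney: 2.4-2.8%, 1.1-1.3%, 0.2% at ρ = 0.3, 0.5, 0.7
- Signed-rank: 4.7-5.3% throughout
- Mann-Whitney at ρ = 0: 4.7-5.2%, so the shortfall comes from the ignored pairing

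**4. Within-group power** (same simulation, mean before of 6; ρ = 0.3/0.5/0.7):

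| Scenario | Mann-Whitney | Signed-rank | Loss (points) |
|---|---|---|---|
| 1.5-point fall, score SD 2.6 | 83/88/92% | 90/97/99.8% | 7/9/8 |
| 1-point fall, score SD 2.6 | 50/51/52% | 63/75/91% | 13/24/39 |
| 1.5-point fall, change SD 2.6 | 93/87/69% | 97/97/96% | 4/10/27 |

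With a mean before of 4 and score SD 2.6, the 1.5-point fall gives 83/87/92% against 90/96/99.6%, and the 1-point fall 50/50/50% against 62/74/90%.

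**5. Between groups (secondary).** Mann-Whitney compares different children here and is valid. The outcome reads most naturally as change, although the sizing text also has "considering a decrease of 36% and a standard deviation of 13" percent. Normal-approximation power is Φ(1.5/(s√(2/40)) − 1.645), with s the SD of the quantity analysed (for ANCOVA, the score SD times √(1−ρ²)):

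| Reading of 2.6 | Raw 30-minute score | Change | Baseline-adjusted ANCOVA |
|---|---|---|---|
| SD of the score | 82.5/82.5/82.5% | 70.4/82.5/95.4% | 85.5/90.9/97.5% |
| SD of change | 92.0/82.5/63.8% | 82.5/82.5/82.5% | 94.0/90.9/87.6% |

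Raw and change analyses differ by 0 to 19 points. On simulated integer scores ANCOVA had 84-97% power: 4-17 points above Mann-Whitney on change and 3-25 above Mann-Whitney on raw scores.

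**The case against.** The strongest reply is that little depends on these tests. The hypothesis test is between groups, the sample size is unaffected, and the error is conservative. At the protocol's own 1.5 points with score SD 2.6, Mann-Whitney still has 83-92% power. The large losses need an assumed 1-point fall, or the change-SD reading at correlation 0.7. All of this stands. It limits the severity, but it does not make an independent-samples test correct for paired data.

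Four further points qualify the remedy:

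- **Other variables.** Heart rate and SaO2 fall under the same sentence and measurement times, so they have the same fault. Sex, reason for check-in and lung occupancy are typed as nominal, and Mann-Whitney does not suit unordered categories even between groups. Both stand.
- **Multiplicity.** Four post-maneuver times, 10 sessions and two groups give up to 4 × 10 × 2 = 80 within-group Wang tests. A correct test brings each one up to about 5% error. This stands, and the session must be named.
- **No test at all.** Reporting within-group change descriptively would also remove the error. That is a fair alternative.
- **Baseline adjustment.** Leaving it out of a randomized comparison is not an error, and simulating rounded normal scores favours a parametric model. Both stand, so adjustment is offered only as an option. Its 3-25 points are not the cost of the pairing error.

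**Conclusion.** The concern holds. As written, the plan applies an independent-samples test to before/after scores of the same children, and the within-group p-values will be wrong whenever those scores are correlated. With assumed correlations of 0.3 to 0.7, the nominal 5% one-sided test runs at about 2.8% down to 0.2%. The power loss is 7 to 9 points for a 1.5-point fall with score SD 2.6, and up to 39 points for an assumed 1-point fall at correlation 0.7. The direction depends only on the correlation being positive; the sizes depend on the stated assumptions.

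The fault is confined to within-group comparisons. The between-group Mann-Whitney test of the Wang score at one named time, with one value per child, is valid, and 40 per group stands. This should be fixed before analysis, but it does not threaten the main comparison.

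**What to change.** **Required.** State that each within-group before/after Wang comparison uses the Wilcoxon signed-rank test, or the Friedman test across several times, and give the rule for zeros and ties. Keep Mann-Whitney U for between-group comparisons only, for ordinal or quantitative variables with one value per child at a named time. Apply the paired rule to heart rate and SaO2 as well, and give the nominal variables a method for categorical data. Name the session and time for any within-group test, or label those results descriptive.

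**Optional.** Compare the 30-minute Wang score between groups with adjustment for the score before the first session (ANCOVA or proportional odds), with Mann-Whitney on change as a sensitivity analysis. At session 1 this estimates the 30-minute effect; at a later session it estimates a cumulative effect, so the session must be named. Do not adjust for pre-session scores from session 2 onward, because they follow treatment.

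**Cost.** Analysis-plan wording only; no new data or participants. Signed-rank assumes roughly symmetric differences. The rule for zeros matters, because 12-22% of simulated pairs had no difference. The optional model adds an assumption for an ordinal score; its simulated type I error was 4.7-5.4%, and the rank-based sensitivity analysis covers that assumption.
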